1.0 BACKGROUND

Mucositis in Children, Adolescents and Young Adults Undergoing Chemotherapy

Oral mucositis, a common and debilitating complication of cancer therapy, is an inflammatory injury to the epithelial and sub-epithelial cells of the oral mucosa. Oral mucositis is thought to develop according to a five-stage model: 1) initiation; 2) up-regulation with generation of messengers; 3) signaling and amplification 4) ulceration with inflammation; and 5) healing, and typically develops 7-14 days into a chemotherapy course (1).

The incidence and severity of oral mucositis depends on many factors including the age and diagnosis of the patient, the specific treatment regimen, underlying oral hygiene and genetic factors (2-4). The incidence of oral mucositis in patients receiving chemotherapy ranges from around 40% of patients receiving myelosuppressive chemotherapy for solid tumors to 70-90% of patients receiving myeloablative therapy prior to stem cell transplant (1, 5, 6). A commonly used grading scale for mucositis is the Common Terminology Criteria for Adverse Events (CTCAE version 4.0) grading scale, where grading is based on both subjective and objective assessments on a 5 point scale (Grade 1 to Grade 5).

Adverse Event	1	2	3	4	5
Mucositis Oral Definition: A disorder characterized by inflammation of the oral mucosal.	Asymptomatic or mild symptoms; intervention not indicated	Moderate pain; not interfering with oral intake; modified diet indicated	Severe pain; interfering with oral intake	Life-threatening consequences; urgent intervention indicated	Death

From the Common Terminology Criteria for Adverse Events (CTCAE) Version 4.0 Published: May 28, 2009 (v4.03: June 14, 2010) U.S. DEPARTMENT OF HEALTH AND HUMAN SERVICES National Institutes of Health National Cancer Institute, p. 19

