2.1 Study Design

This is a randomized controlled trial designed for the purpose of evaluating the efficacy and tolerability of Caphosol therapy for the prevention of oral mucositis (Grade ≥ 2) in children, adolescents and young adults at risk for developing oral mucositis due to their cancer therapy.

Our hypothesis is that by initiating Caphosol at the initiation of chemotherapy administration, we will decrease the incidence and/or severity of oral mucositis (Grade 3 or 4) as well as limit the number of days requiring narcotic analgesics, days of hospitalization and need/duration of total parental nutrition in patients randomized to the treatment group compared to the control group.

Primary Objectives

- To determine if topically administered Caphosol at the initiation of chemotherapy prevents the development of oral mucositis (Grade ≥ 2) in children, adolescents and young adults.
- To determine the tolerability of four times daily Caphosol therapy.

Secondary Objectives

To determine if topically administered Caphosol reduces the severity of oral mucositis, as measured by incidence of severe mucositis (CTCAE v4.0 Grades 3 or 4), age-appropriate pain scores, use of narcotic pain medicine, number of hospital days and number of days on TPN.

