8.1 Definitions

The following definitions are based on the Code of Federal Regulations Title 21 Part 312.32 (21 CFR 312.32(a)).

Adverse Event: Any untoward medical occurrence associated with the use of a drug in humans, whether or not considered drug related.

Suspected Adverse Reaction: Any adverse event for which there is a reasonable possibility that the drug caused the adverse event.

Life-Threatening Adverse Event Or Life-Threatening Suspected Adverse Reaction: An adverse event or suspected adverse reaction is considered “life-threatening” if, in the view of either the investigator or sponsor, its occurrence places the patient or subject at immediate risk of death.

Event Attribution Categories: CTCAE does not define an AE as necessarily ‘caused by a therapeutic intervention.’ The clinical investigator must assign attribution for an adverse event after naming and grading of the event.

Attribution	Description
Unrelated	The AE is clearly NOT related to the intervention
Unlikely	The AE is doubtfully related to the intervention
Possible	The AE may be related to the intervention
Probable	The AE is likely related to the intervention
Definite	The AE is clearly related to the intervention

Unanticipated (unexpected) adverse event or unexpected suspected adverse reaction as defined by the Children’s Hospital Wisconsin (CHW) IRB are those that are *not* already described as potential risks in the consent form, *not* listed in the Investigator’s Brochure or *not* part of an underlying disease.

Expedited (Rapid) Reporting: Certain events may require rapid notification to entities providing patient safety oversight (e.g. IRB) as detailed in Section 8.3.

	Grade 1	Grade 2		Grade 3		Grade 4 and 5
	Expected or Unexpected	Expected	Unexpected	Expected	Unexpected	Expected or Unexpected
Unrelated Unlikely	Not required	Not required	Not required	Not Required	Required	Required
Possible Probable Definite	Not required	Not required	Not Required	Not Required	Required (Non hematologic only)	Required

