10.0 STATISTICAL CONSIDERATIONS

10.1 Statistic Endpoints

The study will not stratify based on diagnosis. The effectiveness of the study will be based on comparing incidence and severity of oral mucositis. Safety and tolerance will be based on the differential incidence of severe adverse events. A continuous sequential boundary will be used to terminate the study if the difference in adverse events occurs at a rate of 10% or greater at the interim analysis performed at the end of study month 3. A continuous sequential boundary will also be constructed for a differential rate of 5%.

An interim analysis will be conducted half way through using the O'Brien-Fleming rule for early stopping because of success.

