10.3 Sample Size Justification

For an alpha of 0.05 and a power of 80%, 48 subjects per group allow detection of a 30% difference in the incidence of oral mucositis (range of oral mucositis is 25% to 50%). Efficacy assessment will occur at study completion.

Twenty subjects per group can detect a 0.6 unit difference in the toxicity scale. This is based on an effect size of 0.90 and a SD of 0.66 units. This is a medium sized clinical difference using Cohen's criteria. This study will serve as a pilot for a larger study. For toxicity, which can only be estimated in the treatment group, 48 subjects in the Caphosol group will allow estimation of a 95% confidence interval of the toxicity of about $\pm 15\%$. Assessment of toxicity will occur once the study enrolls 20 patients to each arm to obtain a preliminary estimate (95% CI) for toxicity and again at study completion (to obtain a more precise estimate). While the study is stopped if it passes the sequential boundary, to obtain an estimate of the toxicity and its 95% Confidence interval (95% CI) both an interim analysis and an analysis at the end of the study will be used to estimate the 95% CI – most precisely at the end of the study.

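### The month-3 safety stopping rule gives a 10% difference but no direction, error rate, power or settled event set, and neither plausible reading of it performs well at about 20 patients per arm

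*Combined protocol and SAP*

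**What the plan says.** Section 10.1 sets the safety measure: "Safety and tolerance will be based on the differential incidence of severe adverse events". It then describes a continuous sequential boundary with this role: "terminate the study if the difference in adverse events occurs at a rate of 10% or greater at the interim analysis performed at", with the look placed three months into the study. A second sentence adds: "A continuous sequential boundary will also be constructed for a differential rate of 5" percent. No direction, error rate, power, boundary shape or minimum number of patients is stated. The efficacy rule in the same section is separate: "An interim analysis will be conducted half way through using the O'Brien-Fleming rule for early stopping because of success".

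Section 10.3 repeats that the study stops if the sequential boundary is passed, without defining it. It also sets a toxicity look by patient count: "Assessment of toxicity will occur once the study enrolls 20 patients to each arm". It says that toxicity can be estimated in the treatment group only.

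The events are described in several places:
- Section 8.0 classifies adverse events by CTCAE v4.0. Section 8.1 defines an adverse event as "Any untoward medical occurrence associated with the use of a drug in humans, whether or not considered drug related".
- The CTCAE table in Section 1.0 has an entry for oral mucositis ("Mucositis Oral Definition: A disorder characterized by inflammation of the oral mucosal"). Section 2.1 makes its severe grades a secondary efficacy outcome, "as measured by incidence of severe mucositis (CTCAE v4.0 Grades 3 or 4".
- Section 8.2 has its own list of stopping-rule events: Grade 4 non-hematologic treatment-related events, and deaths from any cause. It refers to Section 10.3 for the rule.

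**The concern.** A rule that ends a randomized trial should tell the monitoring committee what to compute, in which direction, on which events, and how often it would stop a harmless product. The only numbers here are 10% and 5%. At the size expected by month 3, each corresponds to one to three patients. The committee would have to choose between two readings: an observed gap of 10 points, or a boundary designed to detect a true gap of 10 points. The first can stop the trial by chance; the second would usually miss the harm it is aimed at. Because the difference is unsigned, the literal text also covers an excess in the control arm. Because the event set is not settled, two people applying the rule to the same data could reach opposite decisions.

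**Working it through.** **The plan's own figure.** The plan states no operating characteristic for the safety rule. The nearest figure is the toxicity precision in 10.3, about ±15% with 48 patients. At the worst case, 1.96 × √(0.25/48) = 14.1 points, so it reproduces. It describes one arm at study end and says nothing about a between-arm difference at month 3.

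**Patients at month 3.** The Synopsis gives 48 per arm and a duration of 6-8 months. Assuming uniform accrual, 48 × 3/8 = 18 and 48 × 3/6 = 24 per arm. The 20 per arm in 10.3 belongs to a separate toxicity look but falls inside this range.

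**What the thresholds mean in patients.** Ten points is 2 patients at 18 per arm (11.1 points), 2 at 20 (10.0) and 3 at 24 (12.5; two patients would be 8.3). Five points is 1, 1 and 2 patients.

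**Reading A: observed difference.** Let X and Y be independent binomial(n, p) counts of patients with a severe event on Caphosol and control, with the same true rate p. The chance of a Caphosol excess that crosses is the sum of P(X = x)P(Y = y) over all (x − y)/n ≥ 0.10. The documents give no severe-event rate, so p is an assumption shown over a range.

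| True rate in both arms | 18 per arm | 20 per arm | 24 per arm |
|---|---|---|---|
| 1% | 1.2% | 1.4% | 0.1% |
| 2% | 3.6% | 4.2% | 0.8% |
| 5% | 11% | 13% | 5% |
| 10% | 20% | 21% | 11% |
| 20% | 26% | 28% | 18% |
| 30% | 29% | 30% | 22% |
| 50% | 31% | 32% | 24% |

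The arms are symmetric, so crossing in either direction has twice these chances: at 20 per arm, 25% at a 5% rate and 64% at a 50% rate. For the 5-point boundary and rates of 5-50%, a chance Caphosol excess crosses in 34.5-43.7% of trials at 20 per arm and 14.9-33.3% at 24.

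**Reading B: 10% is the true difference to detect.** One-sided 5% power ≈ Φ(0.10/SE − 1.645), with SE = √{[p₀(1 − p₀) + p₁(1 − p₁)]/n} and p₁ = p₀ + 0.10.
- n = 20, p₀ = 5%: SE = √(0.175/20) = 0.0935; Φ(1.069 − 1.645) = 28%.
- n = 20, p₀ = 50%: SE = √(0.49/20) = 0.1565; Φ(0.639 − 1.645) = 16%.
- n = 24, p₀ = 5%: 32%. n = 24, p₀ = 50%: 17%.

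The normal approximation is rough at 5%, but the order of magnitude is clear.

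**Event set, side by side.** Section 10.1 compares severe adverse events between two arms. Section 8.2 counts only related Grade 4 non-hematologic events and deaths, and refers to 10.3, which defines no boundary. Section 10.3 treats toxicity as a one-arm quantity. These cannot all describe the same rule.

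**If oral mucositis is counted (conditional).** With severe events at 30% on control and 15% on Caphosol, the unsigned rule is crossed in the benefit direction in 69%, 72% and 65% of trials at 18, 20 and 24 per arm. For masking, suppose other severe events are 5% on control and 15% on Caphosol, and severe mucositis 30% and 20%, independent. The combined rates are 1 − 0.95 × 0.70 = 33.5% and 1 − 0.85 × 0.80 = 32.0%. The chance of a harm-direction crossing falls from 47-60% without mucositis to 19-27% with it. All these rates are illustrative.

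**The case against.** **A boundary is named.** The sentence calls for a continuous sequential boundary, and 10.3 repeats the idea. A reader might infer that the plan fixes a bare 10-point trigger and that a safe product would often be stopped. The documents do not establish that: under a properly built boundary, the false-stop rate is whatever the boundary sets. This stands, and the Reading A figures are conditional on that reading. But no boundary is specified, and taking 10% as its design target gives the low power of Reading B.

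**Mucositis is not named in the safety count.** A reader might infer that severe mucositis is inside the rule, so that a working product stops the trial or conceals harm. Section 10.1 assigns mucositis to effectiveness and severe adverse events to safety in consecutive sentences. On the Section 8.2 list, Grade 3 mucositis would not count, and non-fatal Grade 4 would count only if treatment related. The general definition and the CTCAE classification leave the inclusive reading open, but nothing confirms it.

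**Direction may be implied.** The rule sits under safety, success has its own rule, and Section 9.3 lets the committee terminate the study if it is unsafe. An excess on Caphosol is probably what was meant. A sign alone is not enough, though: the one-way figures in the table remain.

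**Low event rates.** If the Section 8.2 list governs, rates near 1-2% are plausible for a rinse expected to have no side effects, and chance crossings at the 10-point threshold are then rare. This stands, and is why the range must be shown.

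**Other safeguards.** Under Sections 8.3 and 9.3 the committee receives all Grade 4 and 5 and unexpected Grade 3 events and can end the trial. It would be wrong to say that patients are unprotected without this rule.

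**Conclusion.** The concern holds as a defect of specification with real consequences for decisions. As an observed-difference rule, it has a substantial chance of a false one-way crossing at assumed rates of 10% or more (11-32% at 18-24 per arm) and a smaller one at 5% (5-13%). As a rule to detect a true 10-point excess, it would miss that excess in roughly two-thirds or more of trials. Neither reading supports a sound decision at month 3, and the text does not choose between them. The disagreement over events among Sections 8.1, 8.2, 10.1 and 10.3 rests on the text alone and needs no assumption.

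The size depends on the assumed event rates and on uniform accrual over 6-8 months. The claims that benefit could trip the rule or offset a true excess of other events depend further on counting mucositis, and should be treated as possibilities to be closed off. The rule can end the trial, so it should be settled before the first safety look.

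**What to change.** In Section 10.1:
1. Define the difference as Caphosol minus control.
2. Replace the 10% and 5% figures with one boundary that has a stated overall false-stop probability (for example, one-sided 5%), and report its power at the planned look over a range of event rates.
3. Say whether that look is set by calendar month or by patient count, and how it relates to the 20-per-arm look in 10.3.

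Across Sections 8.1, 8.2, 10.1 and 10.3, reconcile which events count, correct the cross-reference, and resolve the one-arm statement on toxicity. State explicitly whether oral mucositis is handled only as efficacy. Then check that the chosen events are recorded in both arms: the reporting table in 8.1 does not require expected Grade 3 events, and the diary items in Section 5.0 list side effects for the Caphosol arm only.

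The cost is revised wording, one boundary calculation and possibly some added adverse event recording. The stated ability to act on a 10-point difference will look weaker, because at this sample size it is weak.

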10.2 Statistical Analysis

Comparisons of binary outcomes such as prevention of oral mucositis will use logistic analysis or Fisher's exact test if the numbers are small. Comparisons of the severity of oral mucositis (an ordinal scale) will use the Wilcoxon rank sum test since the data is on a 5 point Likert scale, although there are really only two levels of values. Similarly for the secondary outcome an ordinal pain scale can be treated as an ordinal scale. Length of stay and duration of TPN will use a t-test plus a log transform, if necessary to reduce the skewness of the data. Otherwise the Wilcoxon test will be used.

Although there may be loss to follow-up, we don't expect it because continued

chemotherapy depends on the clearing of the mucositis.

The primary analysis for mucositis will be based on a binary scale (Grade 1 versus Grade ≥ 2 mucositis) because the mucositis essentially has only two clinically pieces to the scale. It also represents common clinical practice.

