2	02/24/2016	
Added updated DSMC language as requested by the MCW DSMC on 1/22/15:
 
This study will be reviewed by the Medical College of Wisconsin Cancer Center Data and Safety Monitoring Committee (MCWCC DSMC). A summary of the MCWCC DSMC activities are as follows:
 
 • Review the clinical trial for data integrity and safety. • Review all unexpected grade 3, and all grade 4, and 5 adverse events, as well as any others requiring expedited reporting as defined in this protocol. (Grades 4 & 5 events must be reported to the DSMC within 5 calendar days of study staff’s knowledge.) • Review all DSM reports. • Submit a summary of any recommendations related to study conduct. • Terminate the study if deemed unsafe for patients. 
A copy of the MCWCC Data and Safety Monitoring Plan and membership roster will be maintained in the study research file and updated as membership changes. The committee will review reports from the study PI twice annually (or more frequently if needed) and provide recommendations on trial continuation, suspension or termination as necessary. Any available DSMC letters will be submitted to the IRB of record as required.
	
YES –
 
Footers/Headers only– updated to protocol v2 Dated 2/24/2016
 
 • Consent Spanish Short Form • HIPAA Adult • HIPAA Adult Spanish • HIPAA Child • HIPAA Child Spanish

SYNOPSIS

Study Title: A Randomized Controlled Trial Investigating Topical Caphosol for Prevention of Oral Mucositis in Children, Adolescents and Young Adults (AYA) Receiving Chemotherapy

Randomized Controlled Trial

[figure not shown]
Number of Patients: A total of 96 patients will enroll to this study with 48 patients in the Caphosol group and 48 patients in the control group.

Study Objectives

- **Primary Objectives**
 - To determine if topically administered Caphosol at the initiation of chemotherapy prevents the development of oral mucositis (Grade ≥ 2) in children, adolescents and young adults.
 - To determine the tolerability of four times daily Caphosol therapy.

- **Secondary Objectives**
 - To determine if topically administered Caphosol reduces the severity of oral mucositis, as measured by incidence of severe mucositis (CTCAE v4.0 Grades 3 or 4), age-appropriate pain scores (FACES and Likert), use of narcotic pain medicine, number of hospital days and duration of total parenteral nutrition (TPN).

Treatment Plan Schema

Caphosol Administration:

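### Optional gain: in Section 10.2, replace Fisher's exact test with Boschloo's for sparse binary secondary outcomes, and name logistic analysis as the single primary test

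*Combined protocol and SAP*

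**What the plan says.** Section 10.2 (Statistical Analysis) states that comparisons of binary outcomes "will use logistic analysis or Fisher's exact test if the numbers are small". It gives no threshold for small numbers and does not tie the fallback to particular endpoints. It adds that "The primary analysis for mucositis will be based on a binary scale", split at Grade 2 or higher.

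Section 2.1 (Study Design) lists a sparser binary outcome among the secondary objectives: severity "as measured by incidence of severe mucositis (CTCAE v4.0 Grades 3 or 4").

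Section 10.3 (Sample Size Justification) states: "For an alpha of 0.05 and a power of 80%, 48 subjects per group allow detection of a 30% difference" in incidence, and notes that the "range of oral mucositis is 25% to 50" percent. It does not give sidedness, the pair of rates, or the test behind the calculation. Section 10.1 adds a half-way efficacy look with an O'Brien-Fleming rule.

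**The concern.** Fisher's test conditions on both margins of the two-by-two table. In this trial the arm sizes are fixed by design, but the total number of events is not. Conditioning on that total makes the test coarse, so its true error rate falls well below the nominal level, most of all when events are few. That is exactly where Section 10.2 sends the analysis to it.

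An unconditional exact test such as Boschloo's keeps the level guarantee and recovers part of the lost power. At stake is power for sparse secondary comparisons, of which Grade 3-4 mucositis is the likely example. A smaller matter is that, with no definition of small, Section 10.2 does not say in advance which test decides the primary endpoint.

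**Working it through.** **Inputs.** 48 per arm (Synopsis: "48 patients in the Caphosol group and 48 patients in the control group"); alpha 0.05 and power 80% (Section 10.3). Two-sided testing is assumed. The documents give no Grade 3-4 rates, so all rates below 25% are assumptions.

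**The plan's own figure.** Take 55% v 25%, mean 0.40:

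n = [1.960·√(2·0.40·0.60) + 0.842·√(0.55·0.45 + 0.25·0.75)]² / 0.30² = 40.7, so 41 per arm.

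With the continuity correction:

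(40.66/4)·[1 + √(1 + 4/(40.66·0.30))]² = 47.1, so 48 per arm.

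This matches the plan and supports the two-sided reading. Exact enumeration gives Fisher's test 80.8% power at 55% v 25%, and 79.9% at 65% v 35%, the lowest of the 30-point pairs checked in 5-point steps.

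**True size of each exact test.** For each of the 49 × 49 possible outcomes (x, y), compute the two-sided Fisher p-value. Size at a common rate p is the sum, over rejected tables, of b(x; 48, p)·b(y; 48, p), where b is the binomial probability.

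| Test | Rejects when | Maximum size |
|---|---|---|
| Fisher | Fisher p ≤ 0.05 | 3.16% (at p = 0.50) |
| Boschloo | Fisher p ≤ 0.0654 | 4.87% |

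Fisher's size is 0.7%, 1.7% and 2.3% at rates of 5%, 10% and 15%. Boschloo's rejection region contains all of Fisher's plus 60 further tables, so its power cannot be lower.

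**What changes under a sparse-data rule.** With equal arms the smallest expected cell is half the total number of events (or of non-events, if fewer). It is below 5 when that total is 9 or less. Among the 60 added tables, those with the fewest events are 5 v 0, 7 v 1, 9 v 2 and 12 v 4, with smallest expected cells of 2.5, 4.0, 5.5 and 8.0. Only the first two, with their mirror images, meet the rule:

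| Events | Fisher p | Boschloo p |
|---|---|---|
| 5 v 0 | 0.056 | 0.035 |
| 7 v 1 | 0.059 | 0.037 |

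The power gain is therefore the probability of those tables (the mirror images add a negligible amount):

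- 15% v 3%: b(7; 48, 0.15)·b(1; 48, 0.03) + b(5; 48, 0.15)·b(0; 48, 0.03) = 0.161·0.344 + 0.120·0.232 = 0.083.
- 20% v 5%: 0.100·0.215 + 0.037·0.085 = 0.025.

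With likelihood-ratio logistic analysis for the non-sparse tables, power goes from about 46% to 54% at 15% v 3%, and from 62% to 64% at 20% v 5%. The gain in points is the same if the Wald version is used for the non-sparse tables, because only these tables change verdict.

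**Primary endpoint.** At the plan's 25% to 50%, the expected count with Grade 2 or higher is 48·0.25 = 12 to 48·0.50 = 24 per arm, so no small-number test is needed. At rates of 25% and 50% the Wald logistic test has true size 4.9% and 5.2%. The likelihood-ratio version ranges from 4.9% to 5.6% over the plan's range, with 5.6% at a 25% rate.

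**The case against.** The strongest reply is that nothing here is wrong. Fisher's test controls the error rate, it is only a fallback, and the 48 per arm reproduces with the continuity correction, which approximates Fisher's test. The sample size therefore already appears to absorb its conservatism. This stands, and it is why the point is optional.

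Four stronger readings are tempting, and the documents do not support them:

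- *The trial loses its stated power.* It does not: Fisher's test still gives about 80% for a 30-point difference.
- *The primary comparison would gain several points.* Head to head at 50% v 25%, Fisher gives 64% and Boschloo 71%. But counts that large should go to logistic analysis, so this gain would not be realised. The same holds at 55% v 25% and, for the most part, at 25% v 10%, where the expected smaller cell is 48·0.175 = 8.4.
- *Severe adverse events are affected too.* Section 10.1 handles these by sequential boundaries, and Section 10.3 by a confidence interval in the Caphosol arm. No Fisher test of them is stated.
- *Logistic analysis is anti-conservative when events are rare.* At a 5% rate the likelihood-ratio test has size 8.9%, but the Wald test has 0.14%. Section 10.2 does not say which is meant.

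It can also be said that an expected-count rule is still a switch made on the data. That is true, but with equal arms it depends only on the pooled event total, not on how events split between arms.

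**Conclusion.** A cheap, optional improvement. For sparse binary secondary outcomes, Boschloo's test gives about 8 points more power at 15% v 3% and 2 to 3 points at 20% v 5%, with no added patients and with its own 5% guarantee. That guarantee belongs to Boschloo's test itself. The logistic test used for larger counts is approximate, and its likelihood-ratio version can slightly exceed 5%.

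The figures rest on 48 evaluable patients in each arm, two-sided 5% testing and assumed event rates. The Fisher ceiling would be 3.5% for a one-sided 5% test and 3.75% at 42 per arm two-sided. It stays at 3.16% if the final level is 0.048 or 0.047 because of the interim look.

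For the primary endpoint, the undefined threshold is mainly a missing detail. A reader might infer that the primary result hangs on a choice made after the counts are known. The text does leave both tests open, but at 25% to 50% incidence the counts are not small by any usual rule.

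**What to change.** In Section 10.2:

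1. Name logistic analysis as the only test for the primary Grade 2 or higher comparison. State whether it is Wald or likelihood ratio, state that it is two-sided, and apply the level left after the O'Brien-Fleming look. Logistic analysis also accommodates the covariate adjustment that Section 4.3 foresees.
2. For binary secondary comparisons such as Grade 3-4 mucositis, use Boschloo's exact test (two-sided, 5%) in place of Fisher's when the smallest expected cell, from the pooled event total, is below 5. Use the named logistic test otherwise.

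The cost is a sentence or two. Boschloo's test is in standard software. Its drawback is that it is less familiar than Fisher's, and like Fisher's it is unadjusted for covariates. Sample size and data collection do not change.
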